11.0 Treatment Evaluation

The International Myeloma Working Group (IMWG) uniform response criteria (Rajkumar et al, 2011) will be used to assess response to therapy.

11.1 Terms and definitions

- **M-protein:** synonyms include M-spike, monoclonal protein and myeloma protein, paraprotein, M-component.

Serum M-protein level is quantitated using densitometry on SPEP except in cases where the SPEP is felt to be unreliable.

- M-proteins migrating in the β -region (usually IgA M-proteins)
- Cases in which the M-spike is so large and narrow on agarose (some specimens >4 g/dL) that they underestimate the actual immunoglobulin level (by greater than 1500 mg/dL) due to technical staining properties of the agarose gel.
- Cases in which there are multiple peaks of same monoclonal protein (aggregates or dimers)

If SPEP is not available or felt to be unreliable (above examples) for routine M-protein quantitation, then quantitative immunoglobulin levels derived from nephelometry or turbidometry can be accepted, with the exception that quantitative IgG may not be used. However, this must be explicitly reported at baseline, and only nephelometry can be used for that patient to assess response. SPEP derived M-spike values and quantitative nephelometric immunoglobulin values cannot be used interchangeably.

Urine M-protein measurement is estimated using 24-h UPEP only. Random or 24 h urine tests measuring kappa and lambda light chain levels are not reliable and are not recommended.

FLC estimation is currently carried out using the serum FLC assay (Freelite, The Binding Site Limited, UK). Patients with kappa/lambda FLC ratio <0.26 are defined as having monoclonal lambda FLC and those with ratios >1.65 as having a monoclonal kappa FLC. The monoclonal light chain isotype is considered the involved FLC isotype, and the opposite light chain type as the uninvolved FLC type.

- **Response terms:** The following response terms will be used: stringent Complete Response (sCR), complete response (CR), very good partial response (VGPR), partial response (PR), Minimal Response (MR), stable disease (SD), and progressive disease (PD).

In addition, for each response category, there will be an “unconfirmed” response category, which will be for internal use, for the purpose of guiding decision making and test ordering. These designations will be applied at the time of the first measurement at which the quantitative aspect of the response category has been satisfied without the confirmation step having been satisfied. The designation “u” will precede the standard abbreviations, and will include usCR, uCR, uVGPR, uPR, uMR, uPD.

- **Measurable disease:** Patients who have a measurable serum or urine M-protein.
 - Serum M-protein ≥ 1 g/dl
NOTE: Quantitative IgG may not be used for defining measurable disease
 - Urine M-protein ≥ 200 mg/24 h
 - Serum FLC assay: Involved FLC level ≥ 10 mg/dl provided serum FLC ratio is abnormal

- Bone marrow plasma cells $\geq 30\%$

The serum free light chain (FLC) assay is of particular use in monitoring response to therapy in patients who have oligo-secretory or non-secretory disease and **should be used in assessing response only if the baseline serum and/or urine M proteins are not “measurable” as above, and the baseline level of the involved FLC is “measurable.”** When using this assay, it is important to note that the FLC levels vary considerably with changes in renal function and in patients with renal insufficiency, the levels of both the kappa and lambda may remain elevated, but the ratio normalizes with achievement of CR. Thus, both the level of the involved and the uninvolved FLC isotype (i.e., the involved/uninvolved ratio or involved-uninvolved difference) should be considered in assessing response. *Patients included on the study on the basis of FLC alone (i.e., no measurable serum/urine m-spike) should be the only ones who are evaluated using FLC response criteria. The others should follow usual criteria and ignore FLC results with the exception of defining stringent complete response.*

- **Evaluable disease:** Patients who do not have a “measurable” serum M-spike, serum free light chain, or urine M-spike.
- **Oligosecretory myeloma:** Patient with multiple myeloma who has NEVER had “measurable” serum M-spike or urine M-spike, but has had a detectable monoclonal protein in his/her serum and/or urine and/or measurable serum free light chain.
- **Non-secretory myeloma:** Patient with multiple myeloma who has NEVER had a detectable monoclonal protein in his/her serum and/or urine.

11.2 Clarification of test indications

Listed below are the minimal required tests required to assess response based on the characteristics of their disease at on study.

Table 11.21: Tests Required to Assess Response (Must Be Done at Each Disease Measurement Visit Except as Indicated^{1,2})

On Study Baseline Value	SPEP ⁴	24 hr UPEP ²	Ig FLC	BM Bx
Serum monoclonal protein ≥ 1 g/dl, and urine M-spike ≥ 200 mg/24 hrs	X	X		
Serum monoclonal protein ≥ 1 g/dl, but urine M-spike < 200 mg/24 hrs	X			
Serum monoclonal protein < 1 g/dl, and urine M-spike ≥ 200 mg/24 hrs		X		
Serum monoclonal protein < 1 g/dl, urine M-spike < 200 mg/24 hrs, but involved Ig FLC is ≥ 10 mg/dL			X	
Serum monoclonal protein < 1 g/dl, urine M-spike < 200 mg/24 hrs, involved Ig FLC is < 10 mg/dL, bone marrow $\geq 30\%$ plasma cells				X ³

¹ **SPEP, UPEP, Immunofixation studies of both serum and urine, and Bone marrow biopsy** are required to document CR regardless of registration values, and in addition **FLC measurement and bone marrow immunophenotyping** is required to document sCR. SPEP and UPEP are required to document VGPR regardless of registration values.

² For serum measurable patients, 24 hour urine does not need to be confirmed (i.e. repeated after documented response) for any response category.

³ At a minimum, a bone marrow biopsy should be repeated every 3 months until documented response. Bone marrow biopsy results do not need to be repeated after documented response.

⁴ If serum monoclonal protein is being followed by quantitative immunoglobulin levels derived from nephelometry or turbidometry, quantitative immunoglobulins are required. SPEP is only required to document CR or VGPR.

11.3 Confirmed response

In order to be classified as a hematologic response, confirmation of serum monoclonal protein, serum immunoglobulin free light chain (when primary determinant of response) and urine monoclonal protein (when primary determinant of response) results must be made by verification on two consecutive determinations.

- Bone marrow aspirate and biopsy are **only** required to document CR or sCR, except for patients with evaluable disease **only**, where a bone marrow is required to document all response categories including progression. However, a second confirmatory bone marrow is **not** required to confirm response in any case.
- Radiographic studies are not required to satisfy these response requirements, however, if radiographic studies were performed there should be no evidence of progressive or new bone lesions.

Appropriate tests required to document and confirm response are listed in Table 11.21.

11.4 Bone progression

Caution must be exercised to avoid rating progression on the basis of variation of radiologic technique alone. Compression fracture does not exclude continued response and may not indicate progression. When progression is based on skeletal disease alone, it should be discussed with the Study Chair before removing the patient from the study.

11.5 Response and Progression

Criteria for response and progression are listed in Table 11.51. Progressive disease for all patients as defined in Table 11.51.

Table 11.51

CATEGORY	RESPONSE CATEGORY ^a
Stringent Complete Response (sCR) ^b	
 • CR as defined plus • Normal FLC ratio and • Absence of clonal PCs by immunohistochemistry or 2- to 4-color flow cytometryⁱ
Complete Response (CR) ^b	
 • Negative immunofixation of serum and urine^c and • Disappearance of any soft tissue plasmacytoma and • ≤5% PCs in Bone Marrow and • If the only measurable disease is FLC, a normal FLC ratio^d
Very Good Partial Response (VGPR)	
 • Serum and urine M-component detectable by immunofixation but not on electrophoresis^c or • ≥90% reduction in serum m-component and urine m-component <100 mg/24 h^c • If the only measurable disease is FLC, a ≥90% reduction in the difference between involved and involved FLC levels

CATEGORY	RESPONSE CATEGORY ^a
Partial Response (PR)	
 • If present at baseline, $\geq 50\%$ reduction of serum M-protein and reduction in 24-hour urinary M-protein or to < 200 mg/24hrs • If the only measurable disease is FLC, a $\geq 50\%$ reduction in the difference between involved and involved FLC levels • If the only measurable disease is BM, a $\geq 50\%$ reduction in BM PC's (provided the baseline PC's was $\geq 30\%$) • If present at baseline, $\geq 50\%$ reduction in the size of soft tissue plasmacytomas
Minor Response (MR)	
 • If present at baseline, $\geq 25\%$ but $< 49\%$ reduction of serum M protein and reduction in 24-hour urine M-protein by 50-89% which still exceeds 200mg/24 hours ^c and • If present at baseline, 25-49% reduction in the size of soft tissue plasmacytoma and • No increase in the size or number of lytic bone lesions (development of compression fracture does not exclude response)
Progressive Disease (PD) ^{b, h}	
Increase of 25% from lowest value in any of the following ^{f, g}:
 
 • Serum M-component (absolute increase must be ≥ 0.5 mg/dL) AND/OR • Urine M-component (absolute increase must be ≥ 200 mg/24 hrs) AND/OR • If the only measurable disease is FLC, the difference between involved and uninvolved FLC levels (absolute increase must be > 10 mg/dL) AND/OR • If the only measurable disease is BM, bone marrow PC percentage (absolute increase must be $> 10\%$) ^e 
Or any one or more of the following:
 
 • Development of new bone lesion or soft tissue plasmacytoma or definite increase in the size of existing bone lesions or soft tissue plasmacytoma • Development of hypercalcemia (corrected serum calcium > 11.5mg/dL) that can be attributed solely to the PC proliferative disorder
Stable Disease (SD)	Not meeting criteria for sCR, CR, VGPR, PR, MR or PD

^a All response categories require two consecutive assessments (sCR, CR, VGPR, PR, MR, PD) made at anytime before the institution of any new therapy; sCR, CR, VGPR, PR, MR and SD categories also require no known evidence of progressive or new bone lesions if radiographic studies were performed. Radiographic studies are not required to satisfy these response requirements. Bone marrow assessments need not be confirmed. Each category, except for stable disease, will have a working subcategory of “unconfirmed” [prefix ‘u’] to designate first time point at which response category MAY have been achieved if confirmed.

^b CR patient will need to progress at the same level as VGPR and PR patients to be considered a PD. A positive immunofixation alone is not sufficient.

^c If more than one M protein spikes meet the criteria for measurable disease at baseline, then both need to be followed for response. Otherwise, only follow the measurable M protein spike for response.

^d In patients in whom the only measurable disease is by serum FLC levels: CR in such patients indicates a normal FLC ratio of 0.26-1.65 in addition to the CR criteria listed above.

^e Bone marrow criteria for PD are only to be used in patients without measurable disease by M protein and by FLC.

^f A "25% increase" refers to M protein, FLC and bone marrow results and does not refer to bone lesions, soft tissue plasmacytoma or hypercalcemia. The lowest value does not need to be a confirmed value. If the lowest serum M-component is ≥ 5 g/dL, an increase in serum M-component of ≥ 1 g/dL is sufficient to define disease progression.

^g In the case where a value is felt to be a spurious result per physician discretion (for example, a possible lab error), that value will not be considered when determining the lowest value.

^h Progressive disease should be confirmed. However, treatment may be discontinued for progressive disease that is unconfirmed per physician discretion. In this case, an objective status of PD should be entered on the measurement form and progressive disease should be reported on the event monitoring form.

ⁱ Presence/absence of clonal cells is based upon the k/l ratio. An abnormal k/l ratio by immunohistochemistry requires a minimum of 100 plasma cells for analysis. An abnormal ratio reflecting presence of an abnormal clone is k/l of 4:1 or 1:2.

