13.0 Treatment/Follow-up Decision at Evaluation of Patient

13.1 Categories of response

Patients who are sCR, CR, VGPR, PR, MR, or (or usCR, uCR, uVGPR, uPR, uMR) will continue treatment per protocol. Patients will go off treatment to event monitoring if an MR is not seen after 2 cycles and a PR is not seen after 4 cycles. Confirmation of MR or PR is not required.

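### As printed, the PR row of Table 11.51 gives no percentage for the urine limb, so for patients followed by urine M-protein alone PR is not cleanly separated from MR

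*Combined protocol and SAP*

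**What the plan says.** Section 11.5 makes Table 11.51 the operative definition of response. After an opening condition (disease present at baseline) and a 50% threshold, the PR row reads "reduction of serum M-protein and reduction in 24-hour urinary M-protein or to" below 200 mg/24 h. The 50% stands before the serum term, and no figure follows the urine term. The MR row does give one: "reduction in 24-hour urine M-protein by 50-89% which still exceeds 200mg/24 hours". Section 11.0 states that the IMWG uniform criteria "will be used to assess response to therapy", but does not restate the PR urine figure, and no other section supplies it.

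Patients measurable by urine alone are eligible (3.15), are followed by 24-hour UPEP only (Table 11.21, Section 11.2), and are recorded as a separate group (12.1).

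PR is used in two places:

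- **Secondary endpoint.** The ≥PR rate after 4 cycles (2.21, 16.321) is reported with an exact 95% interval and has no decision rule. A formal response "must be made by verification on two consecutive determinations" (11.3), and footnote a to the table agrees: "All response categories require two consecutive assessments".
- **Lack-of-response rule (7.2, 13.1).** This looks for MR after 2 cycles and PR after 4. Here "Confirmation of MR or PR is not required", and patients with unconfirmed categories ("uPR, uMR) will continue treatment per protocol") stay on treatment. Section 11.1 assigns the unconfirmed label "at the time of the first measurement at which the quantitative aspect of the response category has been satisfied".

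**The concern.** PR ranks above MR, so every PR should be a larger fall than any MR. Without a urine percentage, the printed PR row does not ensure this for a patient whose only measurable protein is in urine. A small fall could then be counted in the ≥PR rate. Because one unconfirmed measurement is enough under 13.1, it could also keep a patient on the three-drug regimen when the protocol means to stop. Confirmation does not fully protect the secondary endpoint, since a second assessment is judged against the same incomplete threshold.

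**Working it through.** The PR urine limb has no stated figure to reproduce, so the check applies the printed rows to a patient followed by urine alone. B is the baseline and V the later value, both in mg/24 h; the fall is (B − V)/B.

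**Inputs.** Table 11.51: PR urine limb is a fall (no percentage) or V < 200; MR urine limb is a 50-89% fall with V > 200; VGPR urine limb, where percentage falls are used, is V < 100. Section 16.12: 37 evaluable patients.

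**Reading A: no percentage on urine.** B = 1000, V = 700: (1000 − 700)/1000 = 30%. This is a reduction, so PR is met; it is below 50%, so MR is not. A 5% fall (V = 950) also meets PR. The higher category is easier to reach than the lower one.

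This needs the serum limb to drop out. The row's opening condition would remove it for a patient with no serum M-protein. For a patient with a serum protein below 1 g/dL, footnote c (follow only the measurable spike) would do so, but that footnote is marked on the CR, VGPR and MR rows and not on the PR row.

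**Reading B: the 50% governs urine too.** Both PR and MR are met when V > 200, V ≥ 0.11B (fall at most 89%) and V ≤ 0.5B (fall at least 50%). The range is non-empty only if 0.5B > 200, that is B > 400.

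| B | Values meeting both PR and MR |
|---|---|
| 400 | none |
| 600 | above 200, up to 300 |
| 1000 | above 200, up to 500 |
| 3000 | 330 to 1500 (0.11 × 3000 = 330) |

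**Reading C: ≥90% or V < 200.** The 90% is inferred from the MR band ending at 89%. PR is reached at max(200, 0.1B): below 200 for B under 2000, and 300 for B = 3000. From B = 1000, falls of 5-49% are neither category, 50% and 70% are MR, and 89% (V = 110) is PR through the 200 limit. PR and MR no longer overlap. One value is left over: V exactly 200 with a fall under 90% is neither PR (below 200) nor MR (above 200).

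**Size on the ≥PR rate.** Each misclassified patient moves it by 1/37 = 2.7 points. For scale only, 2 or 3 patients give 2/37 = 5.4 and 3/37 = 8.1 points. As an illustration, 25/37 = 67.6% (exact 95% CI 50.2% to 82.0%, width 31.8 points); one upgrade gives 26/37 = 70.3% (53.0% to 84.1%).

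**Lack-of-response rule.** Under Reading A, both the cycle-2 and cycle-4 checks could be loosened, because unconfirmed PR continues treatment. Under Reading B the cycle-2 check is not loosened, but an MR-level fall passes the cycle-4 check.

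**Design figures.** With 13 patients (stop at 3 or fewer) then 37 (success at 13 or more), the probability of success is Σ over x = 4 to 13 of P(X = x | 13, p) × P(Y ≥ 13 − x | 24, p). This gives 0.092 at p = 0.25 and 0.856 at p = 0.45; early stopping is 0.584 and 0.093. All match the table under 16.22, and none depends on PR.

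**The case against.** The strongest reply is that this may not be an error in the plan. The stranded wording before the 200 mg limit calls for a preceding percentage, the table breaks just before this row, and a fragment could have been lost when the PDF was read. That stands: it cannot be excluded from the text alone. Against it, the other percentages in the PR and MR rows survived. A second slip in the PR row, which names the involved light chain twice where the PD row has involved and uninvolved, makes careless drafting plausible. It is weak evidence about this phrase, however, because the same slip is in the VGPR row.

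A second reply is that the intended meaning can be recovered: the MR band stops at 89%, the 200 mg limit is printed, and the IMWG criteria are named. This also stands. A reader might infer that no sensible reading separates PR from MR; Reading C does. A reader might also infer that PR is easier than MR for every urine-only patient. The documents support that only where the serum limb does not apply, which the PR row leaves unclear for those with a small serum protein.

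Formal PR carries further conditions: two consecutive assessments, no known new or progressive bone lesions if imaged, and at least a 50% plasmacytoma reduction if one was present.

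**Conclusion.** The point holds in a limited form and is minor; it concerns an endpoint definition. As printed, Table 11.51 gives no urine percentage for PR, and neither literal reading (none, or 50% carried across) keeps PR apart from MR for patients followed by urine alone. The figure ≥90% does, and is probably what was meant.

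The cost of the ambiguity is 2.7 points on a descriptive rate per misclassified patient of 37, against an interval about 32 points wide, plus possible leniency in the 7.2/13.1 checks. The documents do not give the number of urine-only patients, so no expected bias can be stated. It would be tempting to conclude that the ≥PR rate will be inflated. That would require assessors to apply a visibly incomplete phrase in preference to the adjacent MR row and the named criteria, and nothing shows that they would. Nor does the point reach the primary ≥VGPR endpoint, sample size, alpha or power.

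The conclusion assumes that the figure is absent from the source table and, for Reading A, that the serum limb does not apply.

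**What to change.** Check the PR row against the source table first; if the percentage is there, drop the threshold point. If it is absent:

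1. State the PR urine limb as a reduction by ≥90% or to <200 mg/24 h, after checking the 90% against the IMWG criteria named in 11.0.
2. Attach footnote c to the PR row, so that the serum limb is settled for urine-followed patients.
3. Set the MR limit to ≥200 mg/24 h, so that exactly 200 is classified.
4. Correct the free light chain wording to involved and uninvolved in both the VGPR and PR rows.
5. Re-derive urine-based PRs before reporting the ≥PR rate.

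The cost is a few words and marks in one table, plus re-derivation for the urine-measured patients already identified under 12.1. The reported ≥PR rate may fall slightly. At baselines below 400 mg/24 h PR will still be the first category reachable, because a 50% fall already takes the value under 200; that follows from the printed 200 mg limit and not from the missing percentage.

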3.0 Patient Eligibility

3.1 Inclusion Criteria

- 3.11 Diagnosis and previously untreated active multiple myeloma by IMWG diagnostic criteria for multiple myeloma
- 3.12 Age ≥ 18 years.
- 3.13 The following laboratory values obtained ≤ 14 days prior to registration.
- Calculated creatinine clearance (using Cockcroft-Gault equation below)* ≥ 30 mL/min
 - Absolute neutrophil count (ANC) $\geq 1000/\text{mm}^3$
 - Platelet count $\geq 75000/\text{mm}^3$
 - Hemoglobin ≥ 8.0 g/dL
 - Total bilirubin $\leq 1.5 \times \text{ULN}$
 - ALT and AST $\leq 3 \times \text{ULN}$

*Cockcroft-Gault Equation:

$$\text{Creatinine clearance for males} = \frac{(140 - \text{age})(\text{actual body weight in kg})}{(72)(\text{serum creatinine in mg/dL})}$$

$$\text{Creatinine clearance for females} = \frac{(140 - \text{age})(\text{actual body weight in kg})(0.85)}{(72)(\text{serum creatinine in mg/dL})}$$

- 3.14 Prior therapy for the treatment of solitary plasmacytoma is permitted, but >7 days should have elapsed from the last day of radiation.
NOTE: Prior therapy with clarithromycin, DHEA, anakinra, pamidronate or zoledronic acid is permitted. Any additional agents not listed must be approved by the Principal Investigator.
- 3.15 Measurable disease of multiple myeloma as defined by at least ONE of the following:
- Serum monoclonal protein ≥ 1.0 g/dL (see [Section 11.1](#) for definition)
 - >200 mg of monoclonal protein in the urine on 24 hour electrophoresis
 - Serum immunoglobulin free light chain ≥ 10 mg/dL AND abnormal serum immunoglobulin kappa to lambda free light chain ratio.
- 3.16 ECOG performance status (PS) 0 or 1 (See [Appendix I](#))
- 3.17 Provide written informed consent.
- 3.18 Negative pregnancy test done ≤ 7 days prior to registration, for women of childbearing potential only.
- 3.19a Willing to follow strict birth control measures as suggested by the study.
- 3.19a1 Female patients: If they are of childbearing potential, must agree to one of the following:
- Practice 2 effective methods of contraception, at the same time, from the time of signing the informed consent form through 90 days after the last dose of study drug, AND must also adhere to the guidelines of any treatment-specific pregnancy prevention program, if applicable, OR

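### The Minor Response row of Table 11.51 has no free-light-chain line and is not ordered for combined serum and urine disease, although MR is part of the off-treatment rule

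*Combined protocol and SAP*

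**What the plan says.** **Who is eligible and how they are followed.** Section 3.15 gives three alternative routes to measurable disease. The third is a serum FLC of at least 10 mg/dL "AND abnormal serum immunoglobulin kappa to lambda free light chain ratio". Section 11.1 says that patients entered on FLC alone "should be the only ones who are evaluated using FLC response criteria". Table 11.21 marks FLC as the one routine test in their row, and Section 12.1 lists FLC among the four parameters by which response is followed.

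**The scale.** In Table 11.51 the CR, VGPR, PR and PD rows each carry a line for disease measurable only by FLC. The MR row carries none. It asks for a serum fall of at least 25% but under 49%, and a "reduction in 24-hour urine M-protein by 50-89% which still exceeds 200mg/24 hours", and, where a plasmacytoma was present, a "25-49% reduction in the size of soft tissue plasmacytoma", and no growth in lytic lesions. Footnote c, attached to this row, requires both spikes to be followed when both are measurable at baseline. SD is the residual category: "Not meeting criteria for sCR, CR, VGPR, PR, MR or PD".

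**Where MR is used.** Section 13.1, like 7.2, says: "Patients will go off treatment to event monitoring if an MR is not seen after 2 cycles". The sentence continues, after an 'and', with PR not being seen after 4 cycles. The primary endpoint (16.11, 16.311) is VGPR or better on two consecutive evaluations within the first 4 cycles. Its denominator is all eligible, consented, treated patients except major violations.

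**The concern.** A response scale that feeds a treatment decision should have two properties: every eligible patient can be placed on it by the marker used to follow them, and a deeper response never earns a worse category. The MR row appears to fail both. Two patients with the same proportional fall could be labelled differently because one is followed by serum M-protein and the other by FLC. A patient with a larger urine response could be labelled SD while one with a smaller response is labelled MR. Because the label enters the rule in 7.2 and 13.1, the consequence could reach beyond reporting to who continues treatment and, under one reading of that rule, indirectly to the primary endpoint.

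**Working it through.** **1. FLC-only patients.** Rows of Table 11.51 side by side:

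| Row | Line for FLC-only disease? |
|---|---|
| CR | yes |
| VGPR | yes (fall of at least 90% in the FLC difference) |
| PR | yes (fall of at least 50%) |
| MR | none |
| PD | yes |

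An FLC-only patient with a fall of 50% or more is PR or better and is unaffected. One with a fall of, say, 40% meets no row above SD and is not PD, so is SD by default.

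**2. Serum and urine both measurable.** Take a serum fall of 30%. PR fails because serum is below 50%, so MR turns on the urine condition (fall of 50-89% and residual above 200 mg/24 h).

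| Urine, mg/24 h | Fall | Residual above 200? | Category |
|---|---|---|---|
| 1000 to 400 | 600/1000 = 60% | yes | MR |
| 1000 to 150 | 850/1000 = 85% | no | SD |
| 3000 to 240 | 2760/3000 = 92% | yes, but above 89% | SD |

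The two larger falls score worse than the smallest.

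**3. When the urine window is empty.** With baseline U, the residual exceeds 200 only if the fall is below 1 - 200/U. The window is open only if 1 - 200/U is above 0.50, that is, U above 400.
- U = 300: 1 - 200/300 = 33%, empty.
- U = 400: 50%, empty.
- U = 500: 60%, window 50% to under 60%.
- U = 1000: 80%, window 50% to under 80%.

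Urine is measurable from 200 mg/24 h (11.1), so a patient also measurable in serum with baseline urine of 200-400 mg/24 h cannot reach MR.

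**4. Serum edge.** A serum fall from 3.00 to 1.52 g/dL is 1.48/3.00 = 49.3%, which is neither MR (under 49%) nor PR (at least 50%).

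**5. Route to the primary endpoint.** The 'and' in 7.2/13.1 has two readings.
- *Each check acts alone.* A patient without MR after 2 cycles comes off. That patient stays in the denominator and would very likely count as a failure.
- *Both must fail.* Nobody leaves for lack of response before the cycle 4 check. Those then removed have no PR, so they are already primary-endpoint failures. The effect on the primary endpoint is nil, although the MR label still decides which patients without PR continue.

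**6. Scale of the first reading, as illustration only.** The plan's own figures reproduce first. With 13 then 24 patients, the probability of declaring promise is the sum over x1 = 4 to 13 of P(X1 = x1) × P(X2 ≥ 13 - x1). This gives 0.0920 at 0.25 and 0.8560 at 0.45 (Section 16.22: 0.092 and 0.856). Early stopping, P(X1 ≤ 3), is 0.5843 and 0.0929 (stated 0.584 and 0.093).

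Now assume a share s of patients is FLC-only and a fraction l of their would-be successes is lost through removal after cycle 2. The success rate becomes 0.45 × (1 - s × l). Neither s nor l is in the documents.

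| s | l | Success rate | Power |
|---|---|---|---|
| 5% | 10% | 0.448 | 0.851 |
| 10% | 10% | 0.4455 | 0.845 |
| 10% | 25% | 0.439 | 0.828 |
| 20% | 50% | 0.405 | 0.722 |

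**The case against.** **The endpoint is not built on MR.** This stands. A reader might infer that the trial's response rate is distorted by the MR row. The documents do not support that as a flat statement: it needs the reading in which lack of MR after 2 cycles alone removes a patient. Even then, a lost success lowers the success rate and does not inflate the 9% type I error.

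**The numbers affected may be tiny.** This also stands. Assuming 5-15% FLC-only gives 1.9 to 5.6 of 37 patients, and a reader might take that as 2 to 6 patients misjudged. It counts everyone followed by FLC, not those harmed, who must be short of PR at the check, be removed, and otherwise have gone on to VGPR. Assuming 10% FLC-only, 20% of them in the gap and 25% of those later reaching VGPR gives 0.10 × 0.20 × 0.25 × 37 = about 0.2 of a patient.

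**Section 11.1 is narrower than it may look.** It limits who is judged by FLC criteria. It does not say that no other test applies to those patients; Table 11.21 footnote 1 still requires SPEP and UPEP to document VGPR. The gap does not depend on the stronger reading, because no row gives these patients an MR by FLC.

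**'If present at baseline' might waive the M-protein conditions.** Then any FLC-only patient without growth in lytic lesions would be MR whatever the FLC did. That is no more workable a definition.

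**Section 13.1 lists MR but not SD as continuing.** Little should rest on this. The sentence is visibly incomplete, and a patient in SD after cycle 1 must continue to the cycle 2 check. The off-treatment sentence itself is enough.

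**The 49-50% gap may be typographical**, since the plasmacytoma limit in the same row is 25-49%. It is minor.

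**The row may follow the published IMWG criteria that Section 11.0 adopts.** That cannot be checked from the documents. It would not remove the mismatch with this protocol's own eligibility and treatment rule.

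**Conclusion.** The defect holds on the printed text. The MR row gives no definition for one of the three eligible kinds of measurable disease. For patients measurable in serum and urine it is not monotone, and with baseline urine of 200-400 mg/24 h its urine window is empty. Under either reading of 7.2/13.1 the MR label affects who stays on treatment, so this is more than untidy wording.

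The effect on the primary endpoint is conditional and unquantified. It is nil if both checks must fail. If the cycle 2 check acts alone, it is a possible loss of successes. Its size cannot be computed, because the documents give neither the FLC-only nor the mixed share; the power figures above only show how far the answer depends on assumed inputs.

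One further dependency: the PR row prints no percentage for the urine fall, and the classifications above take it as printed. If a 90% threshold was meant (an assumption), some patients with serum falls above 50% would also drop to SD, for example serum down 55% with urine 1000 to 400 mg/24 h.

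**What to change.** Reconcile the MR row of Table 11.51 with Sections 3.15 and 11.1, the PR row and the rule in 7.2/13.1, so that:

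- every marker that can qualify a patient has an MR definition;
- the categories are exhaustive and ordered, so that a deeper response never scores a worse category;
- the serum limits of MR and PR meet without a gap;
- 7.2 and 13.1 state how the 'and' between the cycle 2 and cycle 4 conditions is to be read.

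The thresholds and the off-treatment rule are for the sponsor to set. The cost is wording in the table and in the two sections. No new test is needed: footnote 4 of the test schedule already requires FLC where it is used to assess response.
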